8.0 Criteria for Removal from the Study

Reason to take patients off study include (but are not limited to) the following:

- Progressive disease
- Patient refusal
- Patient non-compliance
- Physician judgment

9.0 Statistical Considerations

This is an open-label, phase II study of SGI-110 in patients with higher risk MDS. The primary endpoint is complete response (CR) in patients with higher risk MDS treated with SGI-110. CR will be first evaluated at any time after the first cycle, then repeated every 3 cycles thereafter as long as the patient continues treatment. A maximum of 100 patients will be treated (3-5 per month).

The method of Thall, Simon, and Estey [19] will be used to futility, monitor toxicity (adverse events and mortality at 3 months). Multc Lean Desktop (version 2.0) was used to generate the stopping boundaries and the OC tables for futility and the command stopbound in Stata for the toxicity monitoring.

Futility Monitoring

The historical data suggested a complete response rate of 10% with the **standard of care treatment (AZA)** and the target response rate with the experimental treatment (SGI-110) is 25% . Given this, we will stop enrollment into this cohort if the observed patients' data suggest that:

$$\Pr(\pi_E > \pi_H + 0.15 | \text{data}) < 0.025$$

Here π_E and π_H are the complete response rate (CRR) for the experimental treatment and historical standard of care treatment, respectively. That is, if at any time during the study we determine that there is a less than 2.5% chance that the average CRR improves over historical rate by more than 15% we will stop enrollment to this cohort. π_E and π_H are assumed to follow a prior of Beta (0.2, 1.8) and Beta(100, 900), respectively. The stopping boundaries for CRR, based on these assumptions and monitoring conditions are found in **Table 3**. We will apply these stopping boundaries in cohorts of 10 starting from the 10th patient. For example, accrual will cease if 0 patients experiences complete response among the first 10 patients treated. The operating characteristics are summarized in **Table 4**.

Table 3. Stopping boundaries for CRR

Number of patients evaluated for complete response	10	20	30	40	50	60	70	80	90
Number of patients with complete response is less than or equal to	0	0-1	0-3	0-5	0-7	0-9	0-11	0-13	0-15

Table 4. Operating characteristics for monitoring CRR

True Complete Response Rate	Early Stopping Probability	Average number of patients treated
0.10	0.9908	28
0.15	0.8238	50
0.20	0.4285	75
0.25	0.1476	90
0.30	0.0464	96
0.35	0.0166	99

Toxicity Monitoring

In addition, we will monitor toxicities (i.e., Grade ≥ 3 non-hematological toxicity) for all the patients treated. The toxicities will be evaluated **at the end of week 12 from the start of treatment**. The probability of toxicity is denoted by P_E . We assume $P_E \sim \text{beta}(0.6, 1.4)$. Our stopping rule is given by the following probability statement: $\Pr(P_E > 0.30 | \text{data}) > 0.95$. That is, we will stop the study if, at any time during the

study, we determine that there is more than 95% chance that the toxicity is more than 30%. The stopping boundaries for toxicities, based on these assumptions and monitoring conditions is found in **Table 5**. We will apply the toxicity monitoring rule in cohort size of 5 (minimum one patient). For example, accrual will cease if 4 patients experience toxicities among the first 5 patients treated. The operating characteristics are summarized in **Table 6**.

Table 5. Stopping boundaries for toxicity monitoring

The number of patients evaluated for toxicities	5	10	15	20	25	30	35	40	45	50	55	60	65	70	75	80	85	90	95
The number of patients with toxicities is greater than or equal to	4	6	8	10	12	14	16	18	19	21	23	25	26	28	30	32	33	35	37

Table 6. Operating characteristics for toxicity monitoring

True Toxicity Rate	Early Stopping Probability	Sample Size		
		25 th percentile	Median	75 th percentile
0.10	0.0008	100	100	100
0.20	0.0158	100	100	100
0.30	0.1879	100	100	100
0.40	0.7741	15	45	90
0.50	0.9947	10	15	30

Mortality rate at 3 months monitoring

In addition, we will monitor the mortality rate at 3 months for all the patients treated. The probability of mortality is denoted by P_E . We assume $P_E \sim \text{beta}(0.2, 1.8)$. Our stopping rule is given by the following probability statement: $\Pr(P_E > 0.10 \mid \text{data}) > 0.95$. That is, we will stop the study if, at any time during the study, we determine that there is more than 95% chance that the mortality rate is more than 10%. The stopping boundaries for mortality rate at 3 months, based on these assumptions and monitoring conditions is found in **Table 7**. We will apply the mortality monitoring rule in cohort size of 10 (minimum one patient). For example, accrual will cease if all 3 patients died among the first 5 patients treated. The operating characteristics are summarized in **Table 8**.

Table 7. Stopping boundaries for mortality monitoring

The number of patients evaluated for mortality	5	10	15	20	25	30	35	40	45	50	55	60	65	70	75	80	85	90	95
The number of patients dead is greater than or equal to	3	4	5	5	6	7	8	8	9	10	10	11	12	12	13	14	14	15	15

Table 8. Operating characteristics for mortality monitoring

True Mortality Rate	Early Stopping Probability	Sample Size		
		25 th percentile	Median	75 th percentile
0.06	0.0111	100	100	100
0.08	0.0444	100	100	100
0.10	0.1291	100	100	100
0.12	0.2751	85	100	100
0.14	0.4759	40	100	100

Statistical Analysis Plan

All patients who received at least 1 dose of the experimental treatment will be included in the intent-to-treat analysis for efficacy and safety. Safety data will be summarized using frequency and percentage, by organ type, grade and attribution. Complete response and overall response rates will be estimated along with the 95% credible intervals. Survival times (overall survival, time to AML transformation and event-free survival) will be estimated using the Kaplan-Meier method for each patient cohort.

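### Mortality look frequency contradicts itself; Tables 4, 6 and 8 count patients evaluated with no read-out delay; no time is set at which a patient without CR counts as evaluated

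*Combined protocol and SAP*

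**What the plan says.** All of this is in Section 9.0 unless another section is named.

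- **Accrual.** "A maximum of 100 patients will be treated (3-5 per month"). No pause in accrual at interim looks is mentioned anywhere.
- **CR (futility).** "CR will be first evaluated at any time after the first cycle, then repeated every 3 cycles thereafter", for as long as treatment continues. Table 3 is indexed by "Number of patients evaluated for complete response", but the worked example reads "accrual will cease if 0 patients experiences complete response among the first 10 patients treated". The last column of Table 4 is headed "Average number of patients treated".
- **Toxicity.** Assessed "at the end of week 12 from the start of treatment". "We will apply the toxicity monitoring rule in cohort size of 5 (minimum one patient"), which agrees with Table 5.
- **Mortality.** Measured at 3 months. The study stops if "at any time during the study, we determine that there is more than 95% chance that the mortality rate is more than 10" per cent; the toxicity rule has the same any-time wording. The text sets cohorts of ten, the worked example concerns three deaths in the first five patients, and Table 7 runs from 5 to 95 in steps of five.
- **Outside Section 9.** Section 7.0 lets CR be reached at any time on treatment after cycle 1. Section 6.0 places marrows at the end of course 1 and/or 2, with course 6 as an example of a later one. Section 4.2 has a six-course continuation rule. None of these is tied to the Table 3 count.

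**The concern.** Tables 4, 6 and 8 tell a review board how quickly accrual would stop if the drug were inactive, too toxic or too lethal. They do that only if the looks they assume are the looks that will be made, and if their sample sizes mean patients treated.

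The mortality text and its tables describe different schedules. The toxicity and mortality outcomes take about three months to read out while 3-5 patients enter each month. The futility rule, the only decision rule on the primary endpoint, does not say who is in its denominator.

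The direction of each rule matters here. Toxicity and mortality stop on high counts, so a pending patient can only add events. Futility stops on low counts, so treating a pending patient as a failure can stop an active drug.

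**Working it through.** **Inputs (Section 9.0).** Boundaries in Tables 3, 5 and 7; priors Beta(0.2, 1.8) for CR with Beta(100, 900) for history, Beta(0.6, 1.4) for toxicity and Beta(0.2, 1.8) for mortality; accrual 3-5 per month; read-outs of 12 weeks and 3 months; maximum 100.

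**Step 1: reproduce the plan with no delay.** The boundary for *n* patients is the smallest *x* with Pr(P > c | x of n) > 0.95, where P | x ~ Beta(a + x, b + n − x) and c = 0.30 (toxicity) or 0.10 (mortality). Tables 5 and 7 reproduce exactly; so does Table 3, by integrating Pr(π_E > π_H + 0.15). For operating characteristics, convolve the surviving count distribution with Binomial(step, p) from look to look and remove the mass that crosses; the removed mass sums to the stopping probability.

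| Table | True rate | Recomputed | Stated |
|---|---|---|---|
| 4 | 10 / 15 / 25% | 0.9908 / 0.8238 / 0.1476; mean N 28.2 / 49.6 / 90.2 | 0.9908 / 0.8238 / 0.1476; 28 / 50 / 90 |
| 6 | 40 / 50% | 0.7785 / 0.9950; medians 45 / 15 | 0.7741 / 0.9947; 45 / 15 |
| 8, looks every 5 | 12 / 14% | 0.277 / 0.473; 25th percentiles 85 / 40 | 0.2751 / 0.4759; 85 / 40 |
| 8, looks every 10 | 12 / 14% | 0.236 / 0.415; 25th percentiles 100 / 50 | as above |

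Table 4 agrees to four decimals. Tables 6 and 8 agree within simulation error, Table 8 only with looks every five. The printed sample sizes are therefore the number evaluated at the crossing look, with every outcome already known.

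**Step 2: entries during a read-out.** 84 days / 30.44 = 2.76 months; × 3 = 8.3 and × 5 = 13.8 patients. For 3 months the range is 9-15.

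**Step 3: patients treated, no pause.** Simulated accrual at 3-5 per month, counting everyone entered by the time of the look. The timing of events within the window is an assumption.

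| | Stated | Looks wait for full windows | Events count on occurrence, uniform over window | Events count on occurrence, all within 4 weeks |
|---|---|---|---|---|
| Toxicity 50%, median | 15 | 23-30 | 19-24 | 16-17 |
| Toxicity 40%, median | 45 | 52-58 | 47-51 | 44-45 |
| Mortality 14%, stopping before 100 enrolled | 0.476 | 0.42-0.45 | 0.45-0.47 | 0.47-0.48 |

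Under waiting, the same trials cross (0.78 at 40% toxicity, 0.47 at 14% mortality); some cross after the 100th patient has entered. Sample-size cells already at 100 do not move.

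**Step 4: CR, two conventions.** CR timing is not in the documents, so both sets of figures rest on assumptions.

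- *Wait for a fixed window of 4, 12 or 24 weeks.* Crossing probabilities stay as in Table 4. Mean treated at a true CR of 10% becomes 30-33, 36-42 or 44-55 (stated 28); at 15%, 51-53, 56-61 or 62-71 (stated 50).
- *Score patients not in CR after cycle 1 as failures.* Stopping at a true 25% becomes 0.17-0.19 if 90% of CRs occur by cycle 1 and the rest at cycle 4, and 0.23-0.27 if 75% do (stated 0.148). With CRs at 1, 4 and 7 months in 40/40/20% of responders it is 0.50-0.64.

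**The case against.** **The tables can be read as correct.** Tables 5 and 7 count patients evaluated, and Tables 6 and 8 are headed only as sample size. Read that way, and with stopping probabilities taken as crossing probabilities, they need no pause. This stands, and it is why relabelling is an acceptable remedy. A reader might infer that the tables hold only if accrual stops at each look; Step 3 shows otherwise, since early events counted on occurrence give nearly the stated sample sizes. Table 4, however, does say treated.

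**The waiting figures are an upper bound.** Both safety rules act at any time. Section 10.0 sends therapy-associated SAEs to the principal investigator within 24 hours and all SAEs to the IND Office within 5 working days. Many events would be known before a window closes. This also stands, although those duties are not written into the stopping rules, and the end-of-week-12 wording points the other way for toxicity.

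**The false-stopping branch is disfavoured by the text.** A reader might infer that a patient without CR after cycle 1 is a failure, or that Table 4 is unreliable altogether. Sections 7.0 and 9.0 let CR count later and call for repeat evaluation, and nothing scores such a patient as a failure. Under waiting, Table 4's probabilities hold and only the mean number treated moves. What remains is that the convention is unstated.

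**The mortality conflict is a wording matter, separate from lag.** True, but the text as written does not produce Table 8.

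**Conclusion.** The point holds in three parts.

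1. **Mortality looks.** The text contradicts its example and Tables 7 and 8. Followed literally, looks every ten lower stopping at 14% mortality from 0.473 to 0.415 and at 12% from 0.277 to 0.236. This needs no timing assumption and is the firmest part.
2. **Read-out delay.** The sample sizes in Tables 4, 6 and 8 are numbers evaluated. If accrual continues, numbers treated at stopping can be higher: from almost no excess up to about 15 patients on the median at 50% toxicity (30 − 15), depending on when events occur and when they are counted.
3. **CR evaluability.** Section 9 leaves it open. Waiting raises the mean number treated; scoring pending patients as failures raises stopping at 25% above 0.148. The direction depends on the convention and the size on CR timing that the documents do not give.

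No boundary in Tables 3, 5 or 7 is wrong. The matter should be fixed before the rules are applied, but it does not invalidate the design.

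**What to change.** 1. Reconcile the mortality look frequency across the text, the worked example and Tables 7 and 8, and make Table 8 match the schedule the sponsor adopts.
2. State that toxicities and deaths count towards Tables 5 and 7 when they occur, against the boundary for the first *n* treated. Because these rules stop on high counts, the same trials cross, only sooner.
3. State whether accrual pauses at looks. If it does not, either relabel the sample sizes as patients evaluated, or re-run Tables 4, 6 and 8 with read-out lag at 3-5 per month, reporting patients treated and the probability of stopping before 100 are enrolled.
4. State that Table 3 applies to the first *n* consecutively treated patients and that patients with CR assessment pending are not scored as failures. The sponsor chooses the evaluation time and restates Table 4 for it.

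**Cost.** Wording in Section 9 and new simulations; the stated numbers treated become less favourable. The CR time is a trade-off. One that misses 5% or 10% of CRs lowers an effective 25% to 0.25 × 0.95 = 0.2375 or 0.25 × 0.90 = 0.225, and crossing rises to 0.20 or 0.26; a longer window treats more patients if the drug is inactive. Pausing instead would be expensive: 19 toxicity looks × 84 / 30.44 = 52.4 months, added to 20-33 months of accrual, gives about 72-86 months, or 1.2-1.4 patients per month.

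### The 3-month mortality rule says cohorts of 10, but its worked example, Table 7 and Table 8 all rest on looks every 5 patients

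*Combined protocol and SAP*

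**What the plan says.** The mortality part of Section 9.0 (*Mortality rate at 3 months monitoring*) puts a Beta(0.2, 1.8) prior on the 3-month death rate. It stops the study when there is "more than 95% chance that the mortality rate is more than 10"%. On when to look, it states: "We will apply the mortality monitoring rule in cohort size of 10 (minimum one patient").

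The illustration that follows is set at 5 patients: "accrual will cease if all 3 patients died among the first 5 patients treated". Table 7 then gives boundaries at 19 sample sizes, 5 to 95 in steps of 5: 3, 4, 5, 5, 6, 7, 8, 8, 9, 10, 10, 11, 12, 12, 13, 14, 14, 15 and 15 deaths or more. Table 8 gives the early stopping probability and the quartiles of sample size for true mortality of 6% to 14%, with a maximum of 100 patients. Nothing elsewhere in the document reconciles the cohort of 10 with the 5-patient example and grid.

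**The concern.** With cohorts of 10, the first look is at patient 10, where the boundary is 4 deaths. The 5-patient example could then never be applied, and 10 of the 19 columns of Table 7 (5, 15, 25 and so on to 95) would have no use.

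The other two monitoring rules in Section 9.0 do not have this problem. Futility is stated in cohorts of 10 and Table 3 has only multiples of 10. Toxicity is stated in cohorts of 5 and Table 5 runs in fives.

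What is at stake is when early deaths are formally reviewed. If 3 of the first 5 patients die, the cohort sentence calls for no look, while the example stops accrual. Table 8 can describe only one of these schedules.

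**Working it through.** **Inputs, all from Section 9.0.** Prior Beta(0.2, 1.8); stop if Pr(P > 0.10 | data) > 0.95; maximum N = 100; boundaries from Table 7; stated operating characteristics from Table 8.

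**Step 1: reproduce Table 7.** After r deaths in n patients the posterior is Beta(0.2 + r, 1.8 + n − r). The boundary is the smallest r for which the posterior probability of a rate above 0.10 exceeds 0.95.

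- n = 5: r = 2 gives 0.920 and r = 3 gives 0.990, so the boundary is 3.
- n = 10: r = 3 gives 0.933 and r = 4 gives 0.987, so the boundary is 4.
- n = 95: r = 14 gives 0.913 and r = 15 gives 0.952, so the boundary is 15.

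All 19 entries agree with Table 7.

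**Step 2: operating characteristics.** An exact binomial recursion carries forward the distribution of deaths among trials not yet stopped. At each look it adds a Binomial(m, p) count for the m new patients, then removes the probability at or above the boundary. The early stopping probability is the sum of what is removed. For example, at p = 0.14 the look at n = 5 removes 10 × 0.14³ × 0.86² + 5 × 0.14⁴ × 0.86 + 0.14⁵ ≈ 0.022. That look does not exist under cohorts of 10.

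| True mortality | Table 8 | Looks every 5 (5–95) | Looks every 10 (10–90) | Table 8 minus every 10 |
|---|---|---|---|---|
| 6% | 0.0111 | 0.0113 | 0.0091 | 0.0020 |
| 8% | 0.0444 | 0.0442 | 0.0365 | 0.0079 |
| 10% | 0.1291 | 0.1272 | 0.1062 | 0.0229 |
| 12% | 0.2751 | 0.2769 | 0.2356 | 0.0395 |
| 14% | 0.4759 | 0.4733 | 0.4145 | 0.0614 |

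Quartiles of sample size (25th/50th/75th):

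| True mortality | Table 8 | Looks every 5 | Looks every 10 |
|---|---|---|---|
| 12% | 85/100/100 | 85/100/100 | 100/100/100 |
| 14% | 40/100/100 | 40/100/100 | 50/100/100 |

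The 85 is telling in itself, since no look falls at 85 on a 10-patient grid. Averaging 80 and 90 does not explain it either: on that grid only 0.236 of trials have stopped by patient 90, so the 25th percentile is 100.

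**Step 3: could another schedule explain Table 8?**

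- Every 10 plus a look at 100: 0.0092, 0.0376, 0.1131, 0.2560, 0.4518. Below Table 8 at every rate.
- After every patient: 0.0287, 0.0774, 0.1776, 0.3380, 0.5327. Well above Table 8.

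**Step 4: could simulation error explain it?** The document does not say how many trials were simulated, so assume 1,000 to 10,000. At 14%, the standard error around 0.4145 is √(0.4145 × 0.5855 / 1,000) = 0.0156, or 0.0049 with 10,000. The gap of 0.0614 is then about 4 to 12 standard errors. The gaps from the every-5 results are all within about 0.6 standard errors.

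**Step 5: beyond the tabulated range.** Table 8 ends at 14%. Taking 20% as an illustrative rate, which is not in the plan, early stopping is 0.915 with looks every 5 and 0.880 with looks every 10. Mean sample size is 41.1 and 44.4. At 14% the mean sample sizes are 73.7 and 76.4.

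**The case against.** The fair counter-argument concerns weight, not fact. The example, Table 7 and Table 8 all point to 5, and the parallel toxicity rule uses 5. Only one number points to 10, possibly carried over from the futility rule, although the document does not show that. A team working from Table 7 would look every 5 anyway. Even under cohorts of 10 the boundaries at the shared looks are identical, and the cost is about 3 more patients: 76.4 − 73.7 = 2.7 at 14% mortality and 44.4 − 41.1 = 3.3 at 20%. That is roughly 2.7 × 0.14 = 0.4 and 3.3 × 0.20 = 0.7 further expected deaths. At true rates up to the 10% threshold, fewer stops are fewer false alarms, not lost protection.

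This stands as a limit on size. It also makes the point one of internal consistency: the tables are correctly computed for looks every 5. It does not remove the conflict, because the cohort-size sentence is the instruction on when to look and can be followed literally.

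The section also speaks of stopping at any point in the study and of a minimum of one patient. These phrases do not settle the matter: the toxicity rule carries the same ones alongside a matching grid, and monitoring after every patient does not reproduce Table 8.

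**Conclusion.** The inconsistency is real. Tables 7 and 8 were computed for looks every 5 patients, and the sentence prescribing cohorts of 10 does not have the stopping probabilities printed in Table 8. Read literally, it lowers early stopping by 0.2, 0.8, 2.3, 4.0 and 6.1 percentage points at true mortality of 6%, 8%, 10%, 12% and 14%. It also moves the first look from patient 5 to patient 10. The statistical effect is modest and the slip is probably editorial. It still needs correcting, because it leaves an operative early-death rule open to two readings that can give opposite decisions on the same data.

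The calculation assumes independent deaths at a constant rate, with every patient's 3-month status known at each look. Attributing the small residual differences from Table 8 to simulation error is also an assumption.

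**What to change.** In the mortality paragraph of Section 9.0, change the cohort size from 10 to 5. The text then agrees with its example, Table 7 and Table 8, and nothing needs recalculating. In the same edit, reword the example as 3 or more deaths among the first 5 patients, since Table 7 is a greater-than-or-equal boundary.

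If looks every 10 were intended:

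- Remove the ten columns at 5, 15, 25 and so on to 95 from Table 7.
- Replace the example with one at 10 patients (4 or more deaths).
- Restate the Table 8 stopping probabilities as 0.0091, 0.0365, 0.1062, 0.2356 and 0.4145, with 25th percentiles of 100 at 12% and 50 at 14%.

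The first route is a small wording change. The second also needs two tables reissued and acceptance of the lower stopping probabilities.
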